13.1.6 Confidentiality and Retention of Study Records

This document contains trade secrets and commercial information that is confidential and may not be disclosed to third parties. Persons to whom this study protocol is disclosed must be informed that all the information herein is confidential and may not be further divulged. These restrictions will apply as well to all future communications if deemed privileged or confidential. Publication of the study results may only be allowed with written permission from the Sponsor.

All information on a participant obtained during the conduct of the study will be kept confidential. Participants will be identified by an anonymized identifier on all samples and study records provided to the Sponsor or designee. In compliance with ICH GCP, the Sponsor's authorized representatives, monitor(s), auditor(s), IEC, and regulatory authority(ies) will be granted direct access to the participant's original trial-related records for verification of clinical trial procedures and/or data, without violating the confidentiality of the participant, to the extent permitted by the applicable laws and regulations. Consent from the participant for disclosure of such information will be obtained in writing in the ICF. In addition, should a participant require medical care or hospitalization during the course of the study, the clinical site may contact the treating physician with the participant's consent, except that consent may not be requested if there is an emergency situation. If the results of the study are published, the participant's identity will remain confidential.

The clinical sites will maintain adequate study records according to applicable regulatory requirements. The Sponsor will be notified prior to the destruction of study records.

13.1.7 Compliance

This study will be conducted in compliance with the protocol, GCP, all applicable regulations, including the Federal Food, Drug and Cosmetic Act, U.S. applicable Code of Federal Regulations (title 21), and any IEC requirements relative to clinical studies. The study will also be conducted in compliance with the recommendations laid down in the most recent version of the Declaration of Helsinki, with the exception that registration of such Phase 1 trials in a publicly accessible database is not mandatory. As required by the Canadian regulatory agency, a Clinical Trial Application (CTA) will be submitted before the beginning of the study and a No Objection Letter (NOL) must be received prior to dosing.

13.1.8 Data Quality Assurance

The Sponsor or its designee will perform the quality assurance and quality control activities of this study; however, responsibility for the accuracy, completeness, security, and reliability of the study data presented to the Sponsor lies with the Investigator generating the data. When applicable, quality assurance procedures will be performed according to the site SOPs.

The study will be monitored according to the site monitoring plan and SOP to ensure that it is conducted and documented properly according to the protocol, GCP, and all applicable regulatory requirements. The Sponsor is entitled to access information about the status of the study and to review the original documents of the study.

The Sponsor may arrange audits as part of the implementation of quality assurance to ensure that the study is being conducted in compliance with the protocol, SOPs, GCP, and all applicable regulatory requirements. In such case, audits will be independent of and separate from the routine monitoring and quality control functions.

- All participant data relating to the study will be recorded on electronic CRFs unless transmitted to the Sponsor or designee electronically (eg, laboratory data). The Investigator is responsible for verifying that data entries are accurate and correct by electronically signing the CRF.
- Guidance on completion of CRFs will be provided in the CRF Completion Guidelines.
- The Investigator must permit study-related monitoring, audits, IRB/EC review, and regulatory agency inspections and provide direct access to source documents.
- Monitoring details describing strategy, including definition of study critical data items and processes (eg, risk-based initiatives in operations and quality such as risk management and mitigation strategies and analytical risk-based monitoring), methods, responsibilities, and requirements, including handling of noncompliance issues and monitoring techniques (central, remote, or on-site monitoring) are provided in the study monitoring plan.
- The Sponsor or designee is responsible for the data management of this study, including quality checking of the data.
- The Sponsor assumes accountability for actions delegated to other individuals (eg, contract research organizations).
- No records may be destroyed during the retention period without the written approval of the Sponsor. No records may be transferred to another location or party without written notification to the Sponsor.

13.1.9 Source Documents

- Source documents provide evidence for the existence of the participant and substantiate the integrity of the data collected. Source documents are filed at the Investigator's site.

- Data entered in the eCRF that are transcribed from source documents must be consistent with the source documents or the discrepancies must be explained.
- The Investigator must maintain accurate documentation (source data) that supports the information entered in the CRF.
- The Sponsor or designee will perform monitoring to confirm that data entered into the CRF by authorized site personnel are accurate, complete, and verifiable from source documents; that the safety and rights of participants are being protected; and that the study is being conducted in accordance with the currently approved protocol and any other study agreements, ICH GCP, and all applicable regulatory requirements.

13.1.10 Study and Site Start and Closure

First Act of Recruitment

The study start date is the date on which the first participant signs informed consent.

Study/Site Termination

The Sponsor or designee reserves the right to close the study site or terminate the study at any time for any reason at the sole discretion of the Sponsor. Study sites will be closed upon study completion. A study site is considered closed when all required documents and study supplies have been collected and a study-site closure visit has been performed.

The Investigator may initiate study-site closure at any time, provided there is reasonable cause and sufficient notice is given in advance of the intended termination.

Reasons for the early closure of a study site by the Sponsor or Investigator may include but are not limited to:

For study termination:

- Discontinuation of further study treatment development

For site termination:

- Failure of the Investigator to comply with the protocol, the requirements of the IRB/EC or local health authorities, the Sponsor's procedures, or GCP guidelines
- Inadequate or no recruitment (evaluated after a reasonable amount of time) of participants by the Investigator

If the study is prematurely terminated or suspended, the Sponsor shall promptly inform the Investigators, the ECs/IRBs, the regulatory authorities, and any contract research organization(s) used in the study of the reason for termination or suspension, as specified by the applicable regulatory requirements. The Investigator shall promptly inform the participant and should ensure appropriate participant follow-up.

13.2 Appendix 2: Clinical Laboratory Tests

- The tests detailed in [Table 7](#) will be performed by the local laboratory at the time points specified in the SoAs.
- Additional tests may be performed at any time during the study as determined necessary by the Investigator or required by local regulations.

Table 7: Protocol-required Safety Laboratory Tests

Serum or urine pregnancy:	β-human chorionic gonadotropin (β-hCG); urine pregnancy test at screening and follow-up, and serum pregnancy test on Day -1 for WOCBP; in the absence of 12 months of amenorrhea, confirmation with at least one FSH measurement (≥ 40 IU/L or mIU/mL or per local threshold for defining postmenopausal state is required.
Hematology:	Hematocrit, hemoglobin, platelet count, RBC count, RBC distribution width, WBC count and differential: 
• Basophils• Eosinophils• Lymphocytes• Monocytes• Neutrophils
Clinical Chemistry:	Albumin, Alkaline phosphatase, ALT, AST, calcium, chloride, creatinine, creatine kinase, estimated glomerular filtration rate (eGFR, calculated using the MDRD equation), gamma-glutamyl transferase, glucose, phosphorus, potassium, sodium, total, direct and indirect bilirubin, total protein, urea (BUN).
Thyroid Panel:	TSH, FT3, FT4
Coagulation:	Prothrombin time (PT, unless not available due to local laboratory reporting standards), activated partial thromboplastin time (aPTT), and international normalized ratio (INR)
Urinalysis:	macroscopic examination, pH, specific gravity, protein, glucose, ketones, bilirubin, occult blood, nitrite, urobilinogen, and leukocytes. Unless otherwise specified, microscopic examination will be performed on abnormal findings.
Serology:	HIV antigen/antibody, HbsAg, HCV antibody, COVID-19 PCR
Urine Drug Screen:	Amphetamines, methamphetamines, methadone, barbiturates, benzodiazepines, cocaine, opiates, methyl-enedioxy methamphetamine (MDMA), methadone, phencyclidine, and tetrahydrocannabinol
Breath Test:	Alcohol
Other:	HbA1c (Only at screening)

Investigators must document their review of each laboratory safety report.

13.3 Appendix 3: AEs and SAEs: Definitions and Procedures for Recording, Evaluating, Follow-up, and Reporting

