3. Women of childbearing potential (WOCBP) including those who had bilateral tubal ligation must be non-pregnant and non-lactating. They must use and commit to continuing to use a double barrier contraception method with acceptable, highly effective contraception methods from screening until study completion, including at least 90 days following the last study drug administration. WOCBP must have a negative pregnancy test result before administration of study drug and must agree not to donate ova (or egg) for at least 30 days after the last dose of study drug administration. Total abstinence from heterosexual intercourse is accepted (when this is in line with the preferred and usual lifestyle of the subject) for at least 6 months before screening and until at least 90 days following the last study drug administration.

4. Postmenopausal women must have had ≥ 12 months of spontaneous amenorrhea (with follicle-stimulating hormone [FSH] ≥ 40 mIU/mL).
5. Surgically sterile women are defined as those who have had a hysterectomy and/or bilateral oophorectomy. Women who are surgically sterile must provide verbal confirmation. See [Section 13.4](#).
6. Male participants who are sexually active with WOCBP (see [Section 13.4](#)) must:
 - a) Agree to use condoms to protect their partners from becoming pregnant during the study (including washout periods) and not to donate sperm for at least 90 days after the last dose of study drug, *and*
 - b) Agree to ensure that they and their partners are routinely using a medically approved contraceptive method. It is important that male participants not impregnate others while in the study.
7. Body weight ≥ 50.0 kg for men and ≥ 45.0 kg for women and body mass index within the range of 18.0-30.0 kg/m² (inclusive).
8. Participants participating in Part 1b must be willing and able to consume the entire high-fat, high-calorie breakfast in the designated timeframe.
9. Participants must understand the nature of the study, must be willing to participate in the study, and must provide signed and dated written informed consent in accordance with local regulations before the conduct of any study-related procedures.
10. Participants must be, in the opinion of the Investigator, able to participate in all scheduled evaluations, likely to complete all required tests, and likely to be compliant.
11. Participants must be fluent in English or French.

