8 STUDY POPULATION

Prospective approval of protocol deviations to recruitment and enrollment criteria, also known as protocol waivers or exemptions, is not permitted.

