8.1 Inclusion Criteria

Participants are eligible to be included in the study only if all the following criteria apply:

1. Healthy, as determined by the Investigator based on a medical evaluation including medical history, physical examination, neurological examination, laboratory tests and cardiac monitoring. A participant with a clinical abnormality or laboratory parameters outside the reference range for the population being studied may be included only if, in the opinion of the Investigator, the finding is:
 - a. not clinically significant according to the Investigator judgement
 - b. unlikely to introduce additional risk to the participant,
 - c. will not interfere with study procedures or confound study results, and
 - d. is not otherwise exclusionary.
2. Population (see [Section 13.4](#)):
 - a. Part 1a and 1b: Men and women, age 18-55 years inclusive at date of screening.
 - b. Part 2: Men and women aged 18-55 years inclusive at date of screening.
Additional cohort: Participants of the additional cohort will be of approximately equal numbers of males and females, with a minimum of 2 of each gender, aged >55-80 years, inclusive.
3. Women of childbearing potential (WOCBP) including those who had bilateral tubal ligation must be non-pregnant and non-lactating. They must use and commit to continuing to use a double barrier contraception method with acceptable, highly effective contraception methods from screening until study completion, including at least 90 days following the last study drug administration. WOCBP must have a negative pregnancy test result before administration of study drug and must agree not to donate ova (or egg) for at least 30 days after the last dose of study drug administration. Total abstinence from heterosexual intercourse is accepted (when this is in line with the preferred and usual lifestyle of the subject) for at least 6 months before screening and until at least 90 days following the last study drug administration.
4. Postmenopausal women must have had ≥ 12 months of spontaneous amenorrhea (with follicle-stimulating hormone [FSH] ≥ 40 mIU/mL).
5. Surgically sterile women are defined as those who have had a hysterectomy and/or bilateral oophorectomy. Women who are surgically sterile must provide verbal confirmation. See [Section 13.4](#).
6. Male participants who are sexually active with WOCBP (see [Section 13.4](#)) must:

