11.6.5 Clinical Safety Laboratory Tests

- See [Section 13.2](#) for the list of clinical laboratory tests to be performed and the SoA ([Section 4.1](#)) for the timing and frequency.
- The Investigator must review the laboratory results, document this review, and record any clinically significant changes occurring during the study as an AE. The laboratory results must be retained with source documents ([Section 10.1](#)).
- All laboratory tests with values considered clinically significantly abnormal during participation in the study should be repeated until the values return to normal or baseline or are no longer considered clinically significant by the Investigator or MM.
 - If clinically significant values do not return to normal/baseline within a period of time judged reasonable by the Investigator, the etiology should be identified, and the Sponsor notified.
 - All protocol-required laboratory tests, as defined in [Section 13.2](#), must be conducted in accordance with the site's standard procedures or SOPs.
 - If laboratory values from non-protocol-specified laboratory tests performed at the institution's local laboratory require a change in participant management or are considered clinically significant by the Investigator (eg, SAE or AE or dose modification), then the results must be recorded.

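### The FSH clause in Protocol Table 7 confirms postmenopausal state without 12 months of amenorrhea, contradicting Inclusion 4 and Appendix 4, which require both 12 months and FSH of at least 40 mIU/mL

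*Protocol*

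**What the plan says.** The pregnancy row of Table 7 (Protocol, Section 13.2, Appendix 2) carries a rule on menopausal status as well as a list of tests. It says that "in the absence of 12 months of amenorrhea, confirmation with at least one FSH measurement" is needed. The threshold is 40 in IU/L or mIU/mL, with an alternative: "per local threshold for defining postmenopausal state is required".

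The entry criteria and the contraception appendix say something else.

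- Inclusion 4, in the Synopsis and again in Section 8.1, asks that postmenopausal women have had at least 12 "months of spontaneous amenorrhea (with follicle-stimulating hormone" of at least 40 mIU/mL).
- Appendix 4 (Section 13.4) defines non-childbearing potential as surgical sterility or postmenopausal state. For the latter it uses the same pair of conditions, and it then asks for no contraception.

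Neither place allows FSH to replace the 12 months, and neither mentions a local threshold. The FSH footnotes to the three Schedules of Assessments only say that the test is done in potentially postmenopausal women to confirm status. SAP Section 7.8 says only that FSH is tested in postmenopausal women and that the results are listed.

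**The concern.** In Table 7 the FSH result stands in for a missing 12 months of amenorrhea. In Inclusion 4 and Appendix 4 it is required on top of the 12 months. The same laboratory result can therefore lead to two different classifications, depending on which page the site has open.

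The classification has consequences. A woman of childbearing potential must use a condom plus a highly effective method from screening until at least 90 days after the last dose. She also has the pregnancy tests that the Schedules of Assessments restrict to such women, including the serum test on Day -1. A woman classed as postmenopausal has neither. Section 5.3 states that there have been no earlier clinical studies of the drug. Women up to 55 can enter every main cohort, and the additional Part 2 cohort takes those over 55, so women near menopause can be enrolled.

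This is a participant-safety matter. It does not affect any endpoint, analysis set or model.

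**Working it through.** No arithmetic applies, and the plan gives no figure to reproduce. The check is a comparison of the two rules.

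| Element | Table 7 (Section 13.2) | Inclusion 4 (Synopsis, 8.1) and Appendix 4 (13.4) |
|---|---|---|
| Amenorrhea | Clause applies when 12 months is absent | At least 12 months, spontaneous |
| FSH | At least one value of 40 or more | 40 mIU/mL or more |
| Link between the two | FSH in place of 12 months | FSH in addition to 12 months |
| Local threshold | Allowed | Not mentioned |

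**Units.** Table 7 gives IU/L or mIU/mL; the other texts give mIU/mL. Since 1 mIU/mL = 0.001 IU per 0.001 L = 1 IU/L, the figure of 40 means the same in both. Units are not part of the conflict.

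**The deciding case.** Take a woman who is not surgically sterile, has under 12 months of amenorrhea, and has a screening FSH of 40 mIU/mL or more.

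1. Under Inclusion 4 and Appendix 4 she fails the amenorrhea condition. No FSH value can make her postmenopausal. She may still enter, but under Inclusion 3, as a woman of childbearing potential with contraception and pregnancy testing.
2. Under Table 7 the clause is triggered and her single FSH value confirms postmenopausal state.
3. The two answers are opposite.

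**Women with 12 months or more.** The Table 7 clause is not triggered, so it does not contradict the other texts. The Schedules of Assessments already call for FSH at screening in these women.

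**Is the conflict resolved elsewhere?** Section 13.2 says the tests "will be performed by the local laboratory at the time points specified in the SoAs", and Section 11.6.5 points to Section 13.2 "for the list of clinical laboratory tests to be performed and the SoA" for when they are done. Both settle timing; neither says which definition of postmenopausal prevails. The SAP gives no definition. No sentence in either document ranks Section 8.1 or 13.4 above Table 7 on this point.

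**The case against.** The strongest reply is that the controlling text is already right. Section 8.1 opens with "Participants are eligible to be included in the study only if all the following criteria apply", and Section 8 adds that advance approval of departures from the entry criteria, "also known as protocol waivers or exemptions, is not permitted". The inclusion criteria on population, surgical sterility and male partners refer to Section 13.4, never to Table 7. Three consistent statements, in the places that decide eligibility and contraception, outweigh one clause in a list of laboratory tests. This stands. It means that a site reading the whole protocol would classify the woman correctly, and it holds the point at minor.

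A second reply is that the clause only makes an FSH test necessary and does not call the result sufficient. Its bracket is also unclosed in the text available, so its structure is not certain. This reply is weaker. The clause speaks of confirmation and of a threshold that defines postmenopausal state, which is the language of classification. Even on the narrow reading it is out of place, because with under 12 months of amenorrhea there is no postmenopausal state to confirm under Inclusion 4.

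Two stronger readings are tempting and should be resisted.

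- A reader might infer that Table 7 widens eligibility, waives contraception, or already misclassifies some share of women. It does not. It contains no waiver, the governing sections are clear, and no frequency of such women can be derived from the documents.
- A reader might infer that the local-threshold option admits women with FSH below 40. That would need a local cut-off below 40, and the documents state none. What can be said is that the option has no counterpart in Inclusion 4 or Appendix 4.

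**Conclusion.** The Table 7 clause is wrong as written. It contradicts the definition of postmenopausal given in the Synopsis, Section 8.1 and Section 13.4, and nothing in the documents reconciles them. Inclusion 4 and Appendix 4 should govern.

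What remains is a risk of misapplication. Staff handling an FSH result could take the rule from a table headed as protocol-required and class a woman with under 12 months of amenorrhea as not of childbearing potential. She would then go without contraception and the restricted pregnancy tests.

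Severity is minor, and confidence in the textual conflict is high. The conclusion assumes that the clause is read in its natural sense, as a means of confirming menopausal status, and that a site might consult Table 7 without checking Section 13.4. How often that would happen cannot be judged from the protocol or SAP.

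**What to change.** In the pregnancy row of Table 7, delete the clause that begins with the absence of 12 months of amenorrhea, together with the local-threshold option. Put in their place:

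> FSH at screening in potential postmenopausal women; postmenopausal = ≥12 months of spontaneous amenorrhea AND FSH ≥40 mIU/mL (Sections 8.1 and 13.4); any woman not meeting both and not surgically sterile is treated as WOCBP.

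This gives one definition throughout and says what to do with every woman who falls short of it. The cost is the wording of one table row. No test or visit is added, because all three Schedules of Assessments already place FSH at screening for potentially postmenopausal women. The SAP needs no change.

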13.3.1 Definition of AE

AE Definition

- An AE is any untoward medical occurrence in a clinical study participant, temporally associated with the use of study treatment, whether or not considered related to the study treatment.
- NOTE: An AE can therefore be any unfavorable and unintended sign (including an abnormal laboratory finding), symptom, or disease (new or exacerbated) temporally associated with the use of study treatment.

Events Meeting the AE Definition

- Any abnormal laboratory test results (hematology, clinical chemistry, or urinalysis) or other safety assessments (eg, ECG, vital signs measurements), including those that worsen from baseline, considered clinically significant in the medical and scientific judgment of the Investigator.
- Exacerbation of a chronic or intermittent pre-existing condition including either an increase in frequency and/or intensity of the condition.
- New condition detected or diagnosed after the informed consent is signed even though it may have been present before the start of the study.
- Signs, symptoms, or the clinical sequelae of a suspected drug-drug interaction.
- Signs, symptoms, or the clinical sequelae of a suspected overdose of either study treatment or a concomitant medication. Overdose per se will not be reported as an AE/SAE unless it is an intentional overdose taken with possible suicidal/self-harming intent. Such overdoses should be reported regardless of sequelae.

Events not Meeting the AE Definition

- Medical or surgical procedure (eg, endoscopy, appendectomy): the condition that leads to the procedure is the AE.
- Situations in which an untoward medical occurrence did not occur (social and/or convenience admission to a hospital).
- Anticipated day-to-day fluctuations of pre-existing disease(s) or condition(s) present or detected at the start of the study that do not worsen.

